#### **5.13.4. Vital Signs and Other Physical Findings**

Vital signs and physical characteristics include systolic blood pressure (SBP), diastolic blood pressure (DBP), pulse, weight, and BMI. Original-scale data will be analyzed. When these

parameters are analyzed as continuous numerical variables, unplanned measurements will be excluded. When these parameters are analyzed as categorical outcomes and/or treatment-emergent abnormalities, planned and unplanned measurements will be included.

The planned analyses described for the laboratory analytes in Section 5.13.3 will be used to analyze the vital signs and physical characteristics, except for the inclusion of a threshold for change in addition to a limit for the definition of treatment-emergent. Table FCAB.5.3 defines the low and high baseline values as well as the criteria used to define treatment-emergence based on post-baseline values.

**Table FCAB.5.3. Categorical Criteria for Abnormal Treatment-Emergent Blood Pressure and Pulse Measurement, and Categorical Criteria for Weight Changes for Adults**

| Parameter  | Low mmHg                                       | High mmHg                                       |
|--|--|---|
| Systolic BP (mm Hg)
(Supine or sitting – forearm at heart level)                  | $\leq 90$ and decrease from baseline $\geq 20$ | $\geq 140$ and increase from baseline $\geq 20$ |
| Diastolic BP (mm Hg)
(Supine or sitting – forearm at heart level)                 | $\leq 50$ and decrease from baseline $\geq 10$ | $\geq 90$ and increase from baseline $\geq 10$  |
| Pulse (bpm)
(Supine or sitting)   | $<50$ and decrease from baseline $\geq 15$     | $>100$ and increase from baseline $\geq 15$     |
| Weight (kg)
(Consistent clothing and timing in relationship to meals and voiding) | (Loss) decrease $\geq 7\%$                     | (Gain) increase $\geq 7\%$                      |

### 5.13.5. Immunogenicity

The frequency and percentage of subjects with preexisting antidrug antibody (ADA) and with treatment-emergent ADAs (TEADA) to LY3375880 will be tabulated.

For subjects who are ADA negative at baseline, TEADAs are defined as those with a titer 2-fold (1 dilution) greater than the minimum required dilution of the assay. For subjects who are ADA positive at baseline, TEADAs are defined as those with a 4-fold (2 dilution) increase in titer compared to baseline. For subjects with TEADA, the time to first TEADA result, titer evolution over time, and the distribution of maximum titers will be described.

All TEADAs will be listed.

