DLQI ^{c,d}	X	X		X	X	X	X	X	X	X	X	X	X	X	X	X	X	X
Itch NRS ^e	X	X		X	X	X	X	X	X	X	X	X	X	X	X	X	X	X
Skin Pain NRS ^e	X	X		X	X	X	X	X	X	X	X	X	X	X	X	X	X	X
C-SSRS “Baseline/Screening”	X																	
C-SSRS “Since Last Visit”		X	X	X	X	X	X	X	X	X	X	X	X	X	X	X	X	X
Self-Harm Supplement Form	X	X	X	X	X	X	X	X	X	X	X	X	X	X	X	X	X	X
Self-Harm Follow-up Form ^f	X	X	X	X	X	X	X	X	X	X	X	X	X	X	X	X	X	X

	Screening	Induction Period								Maintenance Period								Posttreatment Follow-Up
		Period 1				Period 2				Period 3								
Visit Number	1	2	3	4	5	6	7	8	9	10	11	12	13	14	15	16	17	801
Weeks from randomization		0	1	2	4	8	12	16	20	24	28	32	36	40	44	48	52 or ET	60
Days from randomization		0	7	14	28	56	84	112	140	168	196	224	252	280	308	336	364	420
Visit tolerance interval (days)	-8 to -35		±2	±2	±2	±4	±4	±4	±4	±4	±4	±4	±4	±4	±4	±4	±4	±5
Laboratory Assessment																		
12-lead ECG (single)	X																	
Chest x-ray ^g (posterior–anterior and lateral views)	X																	
TB test ^h	X																	
Read PPD if applicable (48–72 hours post-PPD) ⁱ	X																	
Skin punch biopsies ^j (lesional, nonlesional)		X		X		X		X										
Clinical chemistry	X	X		X	X	X	X	X	X	X	X	X	X	X	X	X	X	X
Hematology	X	X		X	X	X	X	X	X	X	X	X	X	X	X	X	X	X
Lipids (fasting) ^k	X						X										X	
Serum pregnancy ^l	X																	
FSH ^m	X																	
HIV, HCV, ⁿ HBV screening tests	X																	
HBV DNA ^o	X				X			X			X			X			X	X
Urinalysis	X	X						X				X						X
Urine pregnancy ^l		X		X	X	X	X	X	X	X	X	X	X	X	X	X	X	X
Pharmacogenetics sample	X																	
Serum IgE (total)		X		X			X										X	
Serum IgE (allergen)		X						X										

	Screening	Induction Period								Maintenance Period								Posttreatment Follow-Up
		Period 1				Period 2				Period 3								
Visit Number	1	2	3	4	5	6	7	8	9	10	11	12	13	14	15	16	17	801
Weeks from randomization		0	1	2	4	8	12	16	20	24	28	32	36	40	44	48	52 or ET	60
Days from randomization		0	7	14	28	56	84	112	140	168	196	224	252	280	308	336	364	420
Visit tolerance interval (days)	-8 to -35		±2	±2	±2	±4	±4	±4	±4	±4	±4	±4	±4	±4	±4	±4	±4	±5
specific) ^p																		
Exploratory long-term storage samples (serum, plasma EDTA)		X		X	X	X		X		X		X		X		X		
Exploratory long-term storage samples: RNA and DNA (epigenetic)		X			X			X									X	
LY3375880 PK Samples ^q		X	X	X	X	X		X		X		X		X			X	X
Immunogenicity samples ^q		X			X			X		X		X		X			X	X
Target engagement samples (Total IL-33)		X		X	X	X		X		X		X		X			X	

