9.4.9. Immunogenicity Assessments

At the visits and times specified in the Schedule of Activities (Section 2), venous blood samples will be collected to determine antibody production against the LY3375880. To interpret the results of immunogenicity, a PK sample will be collected at the same time points as the immunogenicity sample. All samples for immunogenicity should be taken predose. Instructions for the collection and handling of blood samples will be provided by the sponsor. The actual date and time (24-hour clock time) of each sampling will be recorded.

In addition, subjects who were deemed responders at Week 16 may be prompted to collect an immunogenicity sample at the first scheduled visit where loss of response is observed (i.e., EASI-25 was not achieved) in the maintenance period. This will allow an evaluation of ADA status at the time of retreatment for subjects randomized to placebo until loss of response during the maintenance period. To prevent unblinding of treatment regimen, all subjects who are deemed responders at Week 16 will have PK and immunogenicity collected upon loss of response.

Immunogenicity will be assessed by a validated assay designed to detect ADA in the presence of the LY3375880 at a laboratory approved by the sponsor. Antibodies may be further characterized and/or evaluated for their ability to neutralize the activity of LY3375880.

Treatment-emergent ADA positive (TE ADA+) are defined in Section 10.2.6.

Samples will be retained for a maximum of 15 years after the last subject visit, or for a shorter period if local regulations and ethical review boards (ERBs) allow, at a facility selected by the sponsor. The duration allows the sponsor to respond to future regulatory requests related to the LY3375880. Any samples remaining after 15 years will be destroyed.

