When evaluating continuous measures over time, a restricted maximum likelihood-based mixed-effects model of repeated measures (MMRM) will be used. The model will include treatment, baseline disease severity, geographic region, visit, and treatment-by-visit interaction as fixed categorical effects and, if a baseline score for the measure is available, baseline score and baseline score-by-visit interaction as fixed continuous effects. An unstructured (co)variance structure will be used to model the between- and within-subject errors. If this analysis fails to converge, other structures will be tested. The Kenward–Roger method will be used to estimate the degrees of freedom. Type III sums of squares for the least squares means will be used for the statistical comparison; 95% CI will also be reported. Contrasts will be set up within the model to test treatment groups at specific time points of interest. Further details on the use of MMRM will be described in the SAP.

Fisher's exact test will be used for the AEs, discontinuation, and other categorical safety data for between-treatment group comparisons. Continuous vital signs and other continuous safety variables including laboratory variables will be analyzed by an analysis of covariance with treatment and baseline value in the model.

The Kaplan–Meier product limit method will be used to estimate the survival curves for time-to-event variables.

All tests of treatment effects will be conducted at a 2-sided alpha level of 0.05 with no control for multiple comparisons, unless otherwise stated.

Any change to the data analysis methods described in the protocol will require an amendment ONLY if it changes a principal feature of the protocol. Any other change to the data analysis methods described in the protocol, and the justification for making the change, will be described in the clinical study report (CSR). Additional exploratory analyses of the data will be conducted as deemed appropriate.

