10.2.6. Evaluation of Immunogenicity

The frequency and percentage of subjects with preexisting ADA and with TE ADA+ to LY3375880 will be tabulated. TE ADA+ are defined as those with a titer 2-fold (1 dilution) greater than the minimum required dilution if no ADA were detected at baseline (treatment-induced ADA) or those with a 4-fold (2 dilutions) increase in titer compared to baseline if ADA were detected at baseline (treatment-boosted ADA). For the TE ADA+ subjects, time to first TE ADA+ result, distribution of maximum titers, and titer evolution over time will be described. The frequency of neutralizing antibodies will be tabulated in TE ADA+ subjects. The relationship between the presence of antibodies to LY3375880, IL-33 target engagement, PK parameters, efficacy, and safety parameters will be assessed, as well as the potential impact of rechallenge on ADA responses.

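### Time to first treatment-emergent ADA is described only in subjects who become positive, so it ignores censoring and carries no information on risk; the percentage beside it shows risk but falls with dropout and with later first dosing

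*SAP*

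**What the plan says.** SAP 5.13.5 (Immunogenicity) limits the timing summary to subjects who become positive: "For subjects with TEADA, the time to first TEADA result, titer evolution over time, and the distribution of maximum titers will be described". Protocol 10.2.6 has the same restriction: "For the TE ADA+ subjects, time to first TE ADA+ result, distribution of maximum titers, and titer evolution over time will be described". Neither section gives a time origin or a censoring rule.

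Both sections also plan an incidence table. In the SAP: "The frequency and percentage of subjects with preexisting antidrug antibody (ADA) and with treatment-emergent ADAs (TEADA) to LY3375880 will be tabulated". The SAP adds a listing of all TEADAs.

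Protocol 10.2.1 has a general provision that the "Kaplan–Meier product limit method will be used to estimate the survival curves for time-to-event variables". Neither immunogenicity section refers to it, and the SAP's analysis methods do not carry it forward.

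The Schedule of Activities places ADA samples at Weeks 0, 4, 16, 24, 32, 40, 52 and 60. Protocol 9.4.9 adds a sample at first loss of response: "responders at Week 16 may be prompted to collect an immunogenicity sample".

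**The concern.** A time-to-event summary restricted to subjects who had the event is conditional on the outcome. Its distribution depends on when follow-up stopped as well as on how antibodies form, and it does not use the number who stayed negative. The general Kaplan-Meier sentence does not repair this, because nobody is censored within the stated set.

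Follow-up measured from first LY3375880 exposure is unequal. Subjects randomized to an active dose can be sampled for 60 weeks after first dose. Under Protocol 5.1, placebo nonresponders first receive LY3375880 at Week 16 and so have at most 44 weeks. Placebo responders who lose response start later still, and subjects who leave the study have less.

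This matters because Protocol 3.3 and 5.5 attribute the adverse monkey findings (7 of 22 treated animals in the 6-month study) to immunogenicity, and Protocol 10.2.6 intends to relate ADA to PK, efficacy, safety and rechallenge. Those aims need an onset and incidence display that can be read across groups with different follow-up.

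**Working it through.** The plan states no figure for ADA incidence or onset, so there is none to reproduce.

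**Inputs.** Sample weeks and the Week 16 switch are from the Protocol (Schedule of Activities, 5.1), and 50 subjects per arm from Protocol section 10. Incidence, onset shape and retention are assumptions, because the documents give none.

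**1. Median time among positives, constant hazard, full follow-up.** With Week 52 incidence R, the weekly hazard is λ = −ln(1−R)/52 and F(t) = 1 − exp(−λt). Onset is detected at the next sample, so the median is the first sample week s with F(s) ≥ F(last)/2.

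| R by Week 52 | F(60)/2 | F(24) | F(32) | Median |
|---|---|---|---|---|
| 5% | 0.0287 | 0.0234 | 0.0311 | Week 32 |
| 20% | 0.1135 | 0.0979 | 0.1283 | Week 32 |
| 40% | 0.2227 | 0.2100 | 0.2697 | Week 32 |

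The result for 10% is also Week 32. An eightfold range of incidence leaves the median unchanged.

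**2. Same hazard, first dose at Week 16.** Samples then fall 8, 16, 24, 36 and 44 weeks after first dose. With R = 20%, F(44)/2 = 0.1721/2 = 0.0860, F(16) = 0.0664 and F(24) = 0.0979, so the median is 24 weeks. The mean falls from 33.4 to 25.9 weeks. The rate of antibody formation is identical; only follow-up differs.

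**3. Early onset instead.** Suppose a fixed fraction (5% or 40%) ever forms antibodies, with exponential onset, and follow-up ends at Week 16, 24, 52 or 60.
- Mean onset 4 weeks: the median is the Week 4 sample at all four lengths, and the mean is 8.3 to 8.6 weeks.
- Mean onset 8 or 12 weeks: the median is the Week 16 sample throughout. The means run from 10.5 to 13.0 and from 11.4 to 16.6 weeks.
- Mean onset 24 weeks: the median is still the Week 16 sample, but the mean moves from 12.2 to 23.5 weeks.

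The dependence on follow-up is therefore slight when onset is early and grows as onset is slower. The conditional distributions are the same for 5% and 40%.

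**4. Does the tabulated percentage show risk?** Yes. At 50 per group, 20/50 (40%) has an exact 95% CI of 26.4% to 54.8%, and 3/50 (6%) has 1.3% to 16.5%. Fisher's exact test for 40% against 5% has 99.2% power.

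**5. Crude percentage under dropout, common Week 52 horizon.** Let R = 20%, let p(k) be the probability that onset falls between sample k−1 and sample k, and let G(k) be the proportion still in the study at sample k, with exponential dropout. The crude percentage is Σ p(k)G(k).
- p = 0.0170, 0.0493, 0.0315, 0.0304, 0.0294, 0.0423 at Weeks 4, 16, 24, 32, 40, 52.
- Retention 100%: 20.0%.
- Retention 77%: G = 0.980, 0.923, 0.886, 0.851, 0.818, 0.770, giving 17.3%.
- Retention 35%: G = 0.922, 0.724, 0.616, 0.524, 0.446, 0.350, giving 11.5%.

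With only subjects who have at least one post-dose sample in the denominator, the last two become 17.3/0.980 = 17.6% and 11.5/0.922 = 12.4%. Kaplan-Meier censored at the last sample gives about 20% in all three cases.

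**6. Crude percentage under later first dosing, no dropout.** At the same hazard: 1 − 0.8^(60/52) = 22.7% for Week 0 starters and 1 − 0.8^(44/52) = 17.2% for Week 16 starters.

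**The case against.** The strongest reply is that the section already reports risk. The percentage is the risk measure, and onset among positives is a separate descriptor. That stands. A reader might infer that the plan cannot tell a 5% from a 40% antibody risk, but step 4 shows that it can; the limitation belongs to the timing summary alone.

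A reader might also infer that the timing summary always measures length of follow-up rather than speed of onset. Nothing in the documents supports a constant hazard, and under early onset the summary does track onset (step 3). The claim must stay conditional.

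A third tempting reading is that the randomized doses have unequal follow-up by design. They do not: all three active arms start at Week 0 on the same sampling schedule. The built-in inequality concerns placebo subjects who later switch. Among the randomized doses it arises only through dropout, and Protocol 8.1.1 keeps subjects who stop the drug in the study unless there is a separate reason to leave. The retention values in step 5 are illustrations, not forecasts.

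The size is modest. Falling from 20.0% to 17.3% is 1.4 subjects of 50, and the exact 95% CI for 10/50 is about 10% to 34%. The output is descriptive, with no test or decision rule attached. Protocol 3.3 calls the monkey findings generally not predictive for humans and reports generally low Phase 1 titres without clinically evident impact. These points limit the importance but do not make the conditional summary a sound description of onset.

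**Conclusion.** The concern holds in a limited form. Both documents describe time to first TEADA only in positives, so that summary ignores censoring and on its own says nothing about risk. The percentage in the same section supplies the risk, but it falls with dropout and with later first dosing.

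Under a constant hazard, the median among positives is 32 weeks for Week 0 starters and 24 weeks for subjects first dosed at Week 16. On a common Week 52 horizon with 20% true incidence, the crude percentage is about 20%, 17% and 12% at retention of 100%, 77% and 35%, against about 20% for Kaplan-Meier. These sizes rest on assumed hazard, incidence and retention, and on dropout unrelated to ADA. The shift in timing largely disappears if antibodies form within the first weeks. The change is worth making because the estimator stays interpretable under either onset pattern. No primary or secondary efficacy inference is affected.

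**What to change.** In SAP 5.13.5, keep the percentage table, the listing and the titre descriptions for positives. Replace the time-to-first-TEADA description with a Kaplan-Meier cumulative incidence of first TEADA, specified as follows:

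- **Population:** all dosed subjects with a baseline and at least one post-dose ADA sample. For placebo subjects who switch, state which sample before first LY3375880 is the baseline.
- **Clock:** from first LY3375880 dose to the date of the first TEADA sample, censored at the last ADA sample. Use actual sample dates, including the loss-of-response samples, which can fall at visits without a scheduled ADA draw.
- **Induction:** the Week 16 estimate with 95% CI by randomized dose, read at the end of the Week 16 visit window (Day 112 + 4 = Day 116) so that samples taken late in the window count.
- **Later period:** the curve by initial randomized arm regardless of later reassignment, with placebo subjects who switch to LY3375880 shown separately. A Week 52 estimate by dose received is undefined without further rules, because Protocol 5.1 re-randomizes or reassigns many subjects from Week 16.

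The cost is a few sentences and one figure, with no new data and a method the Protocol already names. The limitations to state are that censoring at the last sample assumes dropout is unrelated to ADA, and that onset is known only to within the 4 to 12 weeks between scheduled samples.

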### **5.13.6. Special Safety Topics, including Adverse Events of Special Interest**

In addition to general safety parameters, safety information on specific topics of special interest will also be presented. Additional special safety topics may be added as warranted. The topics outlined in this section include the protocol-specified AESI.

In general, for topics regarding safety in special groups and circumstances, patient profiles and/or patient listings, where applicable, will be provided when needed to allow medical review of the time course of cases/events, related parameters, patient demographics, study drug treatment and meaningful concomitant medication use. In addition to the safety topics for which provision or review of patient data is specified, these will be provided when summary data are insufficient to permit adequate understanding of the safety topic.

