Although the immune-mediated findings in the animal studies are generally not considered predictive for humans and there have been no apparent clinical effects attributable to immunogenicity in Study FCAA, subjects in Study FCAB will continue to be closely monitored for safety events, including allergic/hypersensitivity reactions, injection site reactions, or other events plausibly related to drug immunogenicity. Ongoing monitoring of safety data (including AEs, SAEs, and selected laboratory measurements) will continue throughout the study using blinded data. Interim safety analyses will be conducted to review unblinded safety data if deemed appropriate based on the ongoing blinded monitoring; the unblinded analyses will be conducted and reviewed by an internal assessment committee composed of personnel who do not have direct site contact or data entry/validation responsibilities.

More information about the known and expected benefits, risks, SAEs, and reasonably anticipated AEs of LY3375880 will be found in the Investigator's Brochure (IB).

4. Objectives and Endpoints

Table FCAB.2 shows the objectives and endpoints of the study.

Table FCAB.2. Objectives and Endpoints

Objectives	Endpoints
Primary 
 To compare the efficacy of LY3375880 to placebo as measured by IGA at Week 16 in the treatment of subjects with moderate-to-severe AD. 	
 Proportion of subjects achieving IGA of 0 or 1 with a ≥ 2-point improvement at Week 16.
Secondary 
 To compare the efficacy of LY3375880 to placebo as measured by improvement in signs and symptoms at Week 16 and 52 in the treatment of subjects with moderate-to-severe AD. To characterize the PK of LY3375880 in subjects with moderate-to-severe AD 	
 Proportion of subjects achieving at Week 16 
 EASI-50 EASI-75 EASI-90 SCORAD-75 SCORAD-90 IGA of 0 Mean change from baseline to Week 16 in 
 EASI SCORAD Proportion of subjects achieving IGA of 0 or 1 at Week 52 Serum PK Data

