9.2.2. Adverse Events of Special Interest

Injection site reactions and allergic/hypersensitivity reactions are AEs of special interest. In the event of an injection site reaction or allergic/hypersensitivity reaction, additional questions will be triggered in the eCRF to provide further details regarding the reaction.

In the event of anaphylaxis or generalized urticaria, additional laboratory samples should be collected after the subject has been stabilized (ideally 1 to 2 hours, and no more than 12 hours after the event), whenever possible. Follow-up samples should be obtained at the next scheduled visit or after 4 weeks, whichever is later. Specific instructions for the collection and handling of samples will be provided by the sponsor.

9.2.3. *Complaint Handling*

Lilly collects product complaints on IPs and drug delivery systems used in clinical studies to ensure the safety of study participants, monitor quality, and to facilitate process and product improvements.

Subjects will be instructed to contact the investigator as soon as possible if he or she has a complaint or problem with the IP so that the situation can be assessed.

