The frequency and percentages of patients with TEAEs will be summarized by treatment using MedDRA PT nested within SOC. Events will be ordered by decreasing frequency within SOC. A common TEAEs (at least reported by 5% of patients) summary will also be provided. As an additional table or figure, the percentages of patients with TEAEs will be summarized by treatment using MedDRA PT (without regard to SOC). Events will be ordered by decreasing frequency within PT. The frequency and percentages of patients with TEAEs by maximum severity will also be summarized by treatment using MedDRA PT nested within SOC.

Fisher's exact test will be performed to compare percentages for each LY3375880 dose group and Placebo at both the SOC and PT levels.

Listings will be presented for all AEs, all SAEs, all AEs leading to death, all AEs leading to study drug temporary interruption, and all AEs leading to discontinuation from the study.

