### 5.13.6.3. Infections

Infections will be defined using the PTs from the MedDRA Infections and Infestations SOC, with additional terms from the Investigations SOC being used in selected instances, as described below.

Treatment-emergent infections will be analyzed according to various groups of infectious events including:

- all infections
  - all PTs in the Infections and Infestations SOC,
- serious infections
  - all PTs in the Infections and Infestations SOC that are SAEs,
- infections that require therapeutic intervention (antibiotics, antivirals, antifungals, and so on)
  - all PTs in the Infections and Infestations SOC for which there is an antimicrobial concomitant medication associated with that event for that subject,

- herpes zoster
  - specific Lilly-defined PTs from the Herpes Viral Infections high-level term (HLT) in the Infections and Infestations SOC, shown in [Appendix 1](#),
- tuberculosis
  - specific Lilly-defined PTs from the Tuberculous Infections HLT and the Investigations SOC, shown in [Appendix 2](#)
- viral hepatitis
  - all PTs from the Hepatitis Viral Infections HLT (HLT code 10057212) in the Infections and Infestations SOC.

For each infection event, the frequency for each PT will be provided, ordered by decreasing frequency in the LY3375880 highest dose group by infection group: all infections, serious infections (overall and on each approach to identifying SAEs), infections that require therapeutic intervention, herpes zoster infections, tuberculosis, and viral hepatitis.

In addition to the incidence of infectious AEs by MedDRA PT as described above, the number and percentage of subjects with treatment-emergent infectious AEs by treatment group will be summarized and listed.

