#### **5.13.6.4. Allergic Reactions/Hypersensitivities**

A search will be performed using the current MedDRA version 20.0 SMQs to search for relevant events, using the following queries:

- Anaphylactic reaction SMQ (20000021)
- Hypersensitivity SMQ (20000214)
- Angioedema SMQ (20000024)

Events that satisfy the queries will be listed, by temporal order within patient ID, and will include SOC, PT, SMQ event categorization including detail on the scope (narrow or broad), reported AE term, AE onset and end dates, severity, seriousness, outcome, etc.

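### The SAP says it covers the protocol's adverse events of special interest, but it has no injection site reaction analysis and only a listing for hypersensitivity, so no output counts subjects with either event by arm.

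*SAP*

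**What the plan says.** Protocol 9.2.2 states: "Injection site reactions and allergic/hypersensitivity reactions are AEs of special interest". For either type, "additional questions will be triggered in the eCRF to provide further details regarding the reaction". Protocol 3.3 links them to possible immunogenicity: "subjects in Study FCAB will continue to be closely monitored for safety events, including allergic/hypersensitivity reactions, injection site reactions".

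SAP 5.13.6 says of its own content: "The topics outlined in this section include the protocol-specified AESI". Its subsections are hepatic tests, renal function, infections (including potential opportunistic infections), allergic reactions/hypersensitivities, the C-SSRS and the self-harm forms.

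SAP 5.13.6.4 searches three standardised MedDRA queries (SMQs): anaphylactic reaction, hypersensitivity and angioedema. The one output it specifies is a listing: "Events that satisfy the queries will be listed, by temporal order within patient ID".

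For all treatment-emergent events, SAP 5.13.2 adds: "Fisher's exact test will be performed to compare percentages for each LY3375880 dose group and Placebo at both the SOC and PT levels".

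SAP 5.13 directs the reader to Section 5.13.5 for AESIs. That section is Immunogenicity; the AESI section is 5.13.6.

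**The concern.** The SAP's statement of coverage is not borne out by the section it introduces. One protocol AESI has no analysis of its own. The other is retrieved by a defined search, but the result is never tabulated by arm.

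These are the two event types the protocol singled out, after animal toxicity that it attributes to antidrug antibodies. The natural first question is how many subjects in each arm had at least one injection site reaction, and how many had at least one hypersensitivity event. The plan as written does not answer it. PTs divide the group into parts, and an SOC can mix it with unrelated events.

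Two further uses suffer. Protocol 10.2.6 plans to relate antibody status to safety, which is harder without a defined per-subject AESI variable. The extra eCRF detail on each reaction has no described analysis. If the term set is chosen only after the unblinded interim review planned in SAP 5.16, it is also weaker evidence than one fixed beforehand.

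**Working it through.** **Text check**

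| Item | Injection site reactions | Hypersensitivity | Infections (not a protocol AESI) |
|---|---|---|---|
| Named AESI in Protocol 9.2.2 | Yes | Yes | No |
| Own subsection in SAP 5.13.6 | None | 5.13.6.4 | 5.13.6.3 |
| Term set defined | No | Three SMQs | Yes |
| Grouped n (%) by arm | No | No, listing only | Yes |
| General PT and SOC tests (SAP 5.13.2) | Yes | Yes | Yes |

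The infections entry rests on SAP 5.13.6.3: "the number and percentage of subjects with treatment-emergent infectious AEs by treatment group will be summarized and listed". The SAP text available stops within Appendix 3, but 5.13.6 refers to no appendix for injection site reactions.

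**Illustration of what grouping changes**

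The plan gives no figure for AESI detection, so there is none to reproduce. As a check on the method, the plan's own power statement (36% versus 8%; 50 per arm in Protocol 10) gives 91.4% by exact enumeration, which agrees with the stated minimum of 90%.

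Inputs: 50 per arm from Protocol 10; two-sided Fisher test at 0.05. The event rates, background rates and term splits are assumptions and are not in the documents.

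Formula: power = Σ over (i, j) of Bin(i; 50, p₁) × Bin(j; 50, p₀) × 1[Fisher p ≤ 0.05].

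1. *Grouped event* (at least one reaction):
   - 30% vs 4%: 93%
   - 20% vs 4%: 59%
   - 10% vs 2%: 19%
   - 10% vs 4%: 9%

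2. *Single term at 20% vs 4%*:
   - Even split over four non-overlapping terms: 20/4 = 5% vs 4/4 = 1%, power 2%.
   - One term carrying 75% of reactions in both arms: 0.75 × 20 = 15% vs 0.75 × 4 = 3%, power 40%.
   - At 30% vs 4% the same two cases give 7.5% vs 1%, power 11%, and 22.5% vs 3%, power 79%.

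3. *Whole SOC*, with unrelated events in a proportion b of both arms, independent of reactions. The SOC rate is 1 − (1 − p)(1 − b).

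| b | SOC rates for 20% vs 4% | Power | SOC rates for 30% vs 4% | Power |
|---|---|---|---|---|
| 5% | 24.0% vs 8.8% | 44% | 33.5% vs 8.8% | 83% |
| 10% | 28.0% vs 13.6% | 34% | 37.0% vs 13.6% | 72% |
| 30% | 44.0% vs 32.8% | 16% | 51.0% vs 32.8% | 39% |

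4. *Smallest count that reaches 0.05 with 0/50 on placebo*: 5/50 gives p = 0.056 and 6/50 gives p = 0.027. Six affected subjects divided among several non-overlapping terms would therefore not be flagged at PT level.

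**The case against.** The strongest reply is that these events are not left uncompared. SAP 5.13.2 tests each dose against placebo at SOC level as well as PT level, and an SOC row counts a subject once across its terms. If the injection site terms share one SOC (the documents do not set out the MedDRA hierarchy), a pooled though diluted comparison already exists. This stands. A reader might infer from the gap that injection site terms are tested only one PT at a time, or that a dose-related signal would be hidden. The documents do not support either: the SOC test keeps 44% power at 20% versus 4% with 5% background, and percentages by arm are printed whatever the test shows. The 2% single-term figure also needs an exactly even split over four terms with no subject reporting two.

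The assumed rates may be high. In Protocol 5.5, all treatment-emergent events together occurred in 11/58 (19%) on drug and 8/20 (40%) on placebo in Phase 1, and injection site reactions are not among the commonest events named. Those were healthy volunteers and some were dosed intravenously, so higher rates remain possible, but lower ones must be shown too.

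Listing is not unique to AESIs: SAP 5.13.6.1 also lists hepatic threshold elevations. The infections section promises grouped counts but no grouped test of its own. The contrast is therefore about counts by arm, not about formal testing.

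Protocol 10.2.4 promises summaries of all safety data by treatment group, SAP 5.2.3 gives a generic Fisher method, and SAP 5.13.6 allows topics to be added. None of these defines an AESI group. The option to add topics does not cure the gap, because the same paragraph says the AESIs are already included.

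**Conclusion.** The gap is real and moderate in size. SAP 5.13.6 claims coverage it does not deliver, and if followed as written the plan yields no count by arm of subjects with at least one injection site reaction or at least one hypersensitivity event. Comparison by PT and by SOC remains, so the defect is the missing AESI-specific grouping, not the absence of any comparison.

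Under assumed rates of 20% versus 4%, grouping gives 59% power, against 16% to 44% for an SOC with 30% to 5% background and 2% to 40% for a single term. These figures depend on independent background events and on the assumed splits. At 10% versus 4% no approach has useful power (9% even when grouped), so the case for the change rests mainly on a clear grouped estimate with its interval. The primary endpoint, sample size and design are unaffected.

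**What to change.** In SAP 5.13.6:

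- Add an injection site reaction subsection with a term set fixed before unblinding.
- For each AESI, report n (%) of subjects with at least one event by arm and by maximum severity for the induction period, with each dose's difference from placebo and a 95% CI, or Fisher's exact test.
- Define hypersensitivity as at least one event in the three SMQs combined, with narrow scope as the main display. Keep the existing listing.
- Report the maintenance period descriptively.

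In SAP 5.13, correct the AESI cross-reference from 5.13.5 to 5.13.6.

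The cost is a few extra tables from data already coded, plus some unadjusted safety comparisons. Keeping to two groupings limits these to 2 × 3 doses = 6. Testing an injection site group and each SMQ at both narrow and broad scope would give (1 + 3 × 2) × 3 = 21.
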